6.2.2 Treatment period

The first dose will be on day 1 of cycle 1 and will be considered the start of the treatment period. The starting dose in phase Ib (escalation) of the study will be determined from the dose escalation regimen; for patients entering phase Ib (expansion cohort) and phase II of the study the MTD, or recommended phase II dose, will be the starting dose. Patients in phase Ib will be assigned to cohorts as per instruction from the BI clinical monitor and in consultation with the investigator and site.

06 Jun 2022

Page 90 of 241

Trial Protocol Version 12 $Proprietary\ confidential\ information. @\ 2022\ Boehringer\ Ingelheim\ International\ GmbH\ or\ one\ or\ more\ of\ its\ affiliated\ companies.\ All\ rights\ reserved.$

Safety assessments (safety laboratory tests and vital signs) must be performed prior to dosing on the infusion days in both phase Ib and phase II.

Inclusion and exclusion	Re-check criteria before dosing at C1D1, as per
	section 3.3.2 and 3.3.3.
Randomisation – Phase II only	Randomisation in IXRS.: Randomization may take place up to 3 days prior to the C1D1 if site procedures require advance randomization to accommodate the logistics of dispensing study medication to patients. Sites that use this option must include a copy of site policy/written justification in the ISF and submit a copy to the sponsor. If randomization is performed prior to C1D1, the subsequent visits must be scheduled with reference to C1D1.
Physical examination and body weight	Performed according to Flow Chart - see section 5.2.8.
Vital signs	Performed according to Flow Chart. See section 5.2.8.
	For Phase II Arm B enzalutamide only – vitals performed weekly as per the Flow Chart; however from C4 onwards only at the start of every cycle of treatment on Day 1 until approval of protocol version 10. After approval of protocol version 10 should be done according to standard of care.
ECG – 12 lead (triplicate)	For C1, ECGs to be taken pre-infusion/enzalutamide, and immediately after the end of infusion or one hour after enzalutamide intake at D1, D8 and D15 of the cycle.
	For C2 only ECGs at D8 and D15 of the cycle – preand post-dosing (as described above).
	For C3 ECGs will be performed as described in C1 for on D1, D8 and D15.
	Further ECGs to be taken at C6, C9, C12 and in 12 week intervals only on Day 1, as per the Flow Chart and footnotes – all ECGs taken pre-infusion/enzalutamide, and immediately after the end of infusion, or one hour after enzalutamide intake. See section 5.2.6 .
ECOG	On Day 1 of cycles as per Appendix 10.1 and the Flow Chart.

Doc. No.: c02304008-15

 $Proprietary\ confidential\ information. @\ 2022\ Boehringer\ Ingelheim\ International\ GmbH\ or\ one\ or\ more\ of\ its\ affiliated\ companies.\ All\ rights\ reserved.$

Safety lab parameters	Including haematology, biochemistry, coagulation parameters, urinalysis by dipstick. To be conducted at visit prior to administration of study drug/s according to Flow Chart.
	Fasting glucose and HbA1c only at screening and on Day 1 of cycles according to Flow Chart. See section 5.2.5.
Dispensing of enzalutamide	Enzalutamide to be dispensed at every weekly visit and/or the start of every cycle dependent to which part of the trial the patient has entered. Supply will cover exactly 7 days of treatment, or 28 days of treatment. Spare drug kits will be provided
Administration of enzalutamide	Enzalutamide to be taken daily in the morning preferably at the same time of day.
	On PK sampling days, enzalutamide must be taken in the clinic and should not be taken prior to the visit. See section 4.3 and appendix 10.6.
	For patients also receiving BI 836845; on infusion days (D1, D8, D15 and D22 of every cycle), the enzalutamide dose must be taken in clinic immediately following the start of infusion. For all other non-infusion days the enzalutamide may be taken at home at the same time of the morning.
Administration BI 836845 – Phase Ib and Phase II Arm A only	One hour infusion of BI 836845; duration may be adjusted in cases of infusion reaction or AE. PK/biomarker sampling time-points will be adjusted accordingly to correspond with the end of the infusion time. See appendix 10.6 "Pharmacokinetic sampling time points".
Diary card issue – Phase Ib expansion cohort only	Diary card issued only in expansion cohort at the time of informed consent and at C1 Day 22. Diary card to be completed for 7 days in screening period prior to C1 Day-1 (Day-7 to Day-2), and for 7 days prior to C2 Day 1 (C1 Day 23 to Day 28).
Compliance check of enzalutamide	A compliance check of enzalutamide is to be made weekly at C1D8, C1D15 and C1D22, and weekly throughout C2 and at the start of every cycle thereafter.
	At C2D1, site staff must question the patient as to the date, time and dose of last enzalutamide intake prior to the visit; this information must be recorded in the eCRF.

Doc. No.: c02304008-15

Page 92 of 241

 $Proprietary\ confidential\ information. ©\ 2022\ Boehringer\ Ingelheim\ International\ GmbH\ or\ one\ or\ more\ of\ its\ affiliated\ companies.\ All\ rights\ reserved.$

	In Phase Ib expansion cohort only - Review of diary card and compliance check of enzalutamide taken 7 days prior to C2 D1.
Circulating tumour cells (CTCs)	As per the time-points on the Flow Chart and Appendix 10.6: Prior to study drug administration at C1D1, C2D1, C3D1, C5D1, C7D1 and every 12 weeks thereafter at C10D1, C13D1 onwards (until approval of protocol version 10).
Prostate Serum Antigen (PSA)	Single blood sample collected prior to dosing at C1D1, C3D1 and at the start of the cycle thereafter as per the Flow Chart.
Tumour assessments and bone scans	Every 8 weeks (every 2 cycles) up to week 24 and then every 12 weeks (every three cycles) thereafter from start of study treatment in phase Ib escalation and expansion cohort and from randomisation in phase II, i.e. within 7 days prior to theoretical C3, C5, C7, C10 and onwards. Following implementation of Protocol Version 12 as per standard of care.
	Assessment by modified RECIST criteria version 1.1 (R09-0262) and prostate cancer clinical trials working group (PCWG2) criteria, (R13-1642) see appendix 10.4 and section 5.1.2.1
Adverse event and concomitant therapy	Collection of data throughout study treatment period until after approval of protocol version 10 when only adverse event data will be collected.

Trial Protocol Version 12

Page 93 of 241

Proprietary confidential information. © 2022 Boehringer Ingelheim International GmbH or one or more of its affiliated companies. All rights reserved.

From cycle 3 onwards for phase Ib and phase II – the assessments and dosing schedule will be repeated for all subsequent cycles unless otherwise stated in the Flow Chart, e.g. tumour assessment schedule.

6.2.3 End of trial and follow-up period

During the end of treatment and follow up visits all procedures stated in the Flow Chart should be performed.

End of treatment:

All patients

Safety labs	See section 5.2.5.
Tumour assessments and bone scans	Assessment, if applicable, by modified RECIST criteria version 1.1 (R09-0262) and prostate cancer clinical trials working group (PCWG2) criteria (R13-1642), see appendix 10.4 and section 5.1.2.1. All patients should have a tumour assessment/bone scan at EOT visit regardless of the reason for discontinuation, unless the last evaluation was performed within 4 weeks of EOT
Adverse event	Collection of data.
Compliance check of enzalutamide	Final compliance check for enzalutamide intake.
Termination of trial medication	At end of treatment visit.

Any assessments, for example vital signs, to ensure patient safety should be done as per standard of care.

Additional procedures for patients with end of treatment visit prior to approval of protocol version 10:

Physical examination and weight	Performed as per section 5.2.8.
Vital signs	Performed as per section 5.2.8
ECG – 12 lead (triplicate)	See section 5.2.6.
ECOG performance score	As per Appendix 10.1 and the Flow Chart.

Trial Protocol Version 12

Page 94 of 241

Proprietary confidential information. © 2022 Boehringer Ingelheim International GmbH or one or more of its affiliated companies. All rights reserved.

Circulating tumour cells (CTCs)	See Flow Chart and appendix 10.6 for details.
Prostate Serum Antigen (PSA)	Single blood sample collected as per Flow Chart.
Concomitant medications	Collection of data

Follow-Up Visits:

All patients

Adverse event	Data will be collected through to the last follow up visit.
Safety lab parameters	See section 5.2.5.

Additional procedures for patients with follow up visits prior to approval of protocol version 10:

Physical exam and weight (optional)	Performed as per section 5.2.8
Vitals	Performed as per section 5.2.8
ECG – 12 lead (triplicate)	See section 5.2.6.
ECOG performance score	As per Appendix 10.1 and the Flow Chart.
Concomitant medications	Collection of data
Tumour assessments and bone scans	Assessment, if applicable, by modified RECIST criteria version 1.1 (R09-0262) and prostate cancer clinical trials working group (PCWG2) criteria (R13-1642), see appendix 10.4 and section 5.1.2.1

Doc. No.: c02304008-15

06 Jun 2022

Page 95 of 241

Trial Protocol Version 12 Proprietary confidential information. © 2022 Boehringer Ingelheim International GmbH or one or more of its affiliated companies. All rights reserved.

Patient status	To be collected at every follow-up visit. Information collected on last contact date, start of new anticancer therapy, or death.
Patient completion	Performed as per section 6.1.3.5

Additional follow-up visits:

Until approval of protocol version 10, subsequent follow-up visits will be required where a patient has withdrawn from the study treatment for reasons other than disease progression, or start of further anti-cancer therapy, or death, will continue with follow-up visits at scheduled tumour assessments until one of the above mentioned criteria have been met. Only AE and concomitant medication information will be collected at these visits.

Observation Visits:

Until approval of protocol version 10, patients that have withdrawn from the study participation due to disease progression, or start of other anti-cancer therapy, they will enter an observation period and be contacted every 90 days (3 months).

Patient status	Information collected on last contact date, start of new anti-cancer therapy, or death.
Patient completion	Performed as per section 6.1.3.5

Proprietary confidential information. © 2022 Boehringer Ingelheim International GmbH or one or more of its affiliated companies. All rights reserved.

7. STATISTICAL METHODS AND DETERMINATION OF SAMPLE SIZE

7.1 STATISTICAL DESIGN – MODEL

This is a Phase Ib/II open label trial split into three parts. Phase Ib escalation follows a 3+3 design, and the objective of this phase is to determine the maximum tolerated dose of BI 836845 in combination with enzalutamide. There is also an exploratory expansion cohort in phase Ib; the objective is to evaluate restoration of anti-tumour activity of BI 836845 in combination with enzalutamide. In phase II, patients will be randomised in a 1:1 ratio to two treatment arms: BI 836845 + enzalutamide (Arm A), and enzalutamide alone (Arm B). The objective of phase II is to further explore the anti-tumour activity and safety of BI 836845 in combination with enzalutamide, versus enzalutamide alone, in patients with diagnosed and histologically, or cytologically, confirmed metastatic CRPC that have received and progressed after docetaxel and abiraterone treatment.

7.2 NULL AND ALTERNATIVE HYPOTHESES

As an exploratory Phase Ib/II trial, inferences about the efficacy of BI 836845 in combination with enzalutamide will be based on the magnitude of the observed difference in PFS and other efficacy endpoints (including overall survival), rather than formal hypothesis testing.

7.3 PLANNED ANALYSES

During phase Ib (escalation), cohorts of patients treated with BI 836845 in combination with enzalutamide will be evaluated continuously based on the safety profile in order to determine the MTD and /or recommended phase II dose. This MTD, and /or recommended phase II dose will be used in the phase Ib expansion cohort and in phase II.

Efficacy analyses will include all randomised patients in phase II. For phase Ib expansion cohort PFS will be summarised on cohort level. No comparisons between dose cohorts will be performed for phase Ib escalation.

Safety analyses will be summarized separately for patients treated in phase Ib and phase II. The safety profile for the phase II patients will be compared in a descriptive manner between the BI 836845 in combination with enzalutamide arm, and the enzalutamide only arm.

7.3.1 Primary analyses

The primary analysis of PFS for the phase II will be conducted and reported when approximately 60 patients (out of 80 randomised patients) have progressed or died. However, it may be performed with fewer events after approximately 23 months of the first patient being randomized in the Phase II part. Any additional information collected after the data cut-off for the primary analysis will be part of a revised report.

A Cox proportional hazards model (using Breslow's method for dealing with ties) will be used to analyse PFS for the phase II patients. The model will be used to estimate the hazard ratio of BI 836845 in combination with enzalutamide vs. enzalutamide alone, where a value

Doc. No.: c02304008-15

06 Jun 2022

Page 97 of 241

Trial Protocol Version 12 Proprietary confidential information. © 2022 Boehringer Ingelheim International GmbH or one or more of its affiliated companies. All rights reserved.

of less than one favours BI 836845 in combination with enzalutamide. The estimate of the hazard ratio, its asymptotic two-sided 95% confidence interval and asymptotic two-sided pvalue when testing against a value of one will be displayed. The proportional hazards assumption will also be checked.

The Kaplan-Meier survival rate quartiles (with two-sided 95% confidence intervals found using Greenwood's variance estimate) will be presented for each treatment group. The equality of the survival curves will be tested by the log-rank test at the 5% significance level.

PFS for phase Ib expansion, patients will be summarized separately to phase II patients using descriptive statistics only.

PFS is defined as the time from randomisation for phase II (from the start of treatment for phase Ib) to disease progression in bone based on prostate cancer clinical trials working group (PCWG2) criteria, or soft tissue based on modified RECIST 1.1 (as detailed in Section 5.1.2.1), or death. Patients without image-based progression or death at any time during the study will be censored at the date of their last imaging. Detailed censoring rules will be specified in the TSAP.

For the exploratory expansion cohort, PSA response, defined as a decline in PSA >50% (which is confirmed by a second value 3 to 4 weeks apart), will be used as primary endpoint. Descriptive statistics for PSA response will be provided for all treated patients.

7.3.2 Secondary analyses

The analysis of PFS based on independent review data will be performed in the same way as the primary evaluation on investigator assessments.

Overall survival will be analysed using a Cox proportional hazards model in the same way as the primary endpoint for phase II (see Section 7.3.1). A hazard ratio and 95% confidence interval for BI 836845 in combination with enzalutamide vs. enzalutamide alone will be presented. Kaplan-Meier estimates of overall survival will be plotted by treatment group. A log-rank test will also be performed to compare the survival curves.

The first analysis of overall survival will be performed at the time of primary PFS analysis. The analysis will be updated once all patients have completed the last follow-up visit and/or when an adequate number of patients have died. The time to PSA progression will be analysed using a Cox proportional hazards model in the same way as the primary endpoint for phase II (see Section 7.3.1). In addition, the percentage change from baseline in PSA will be summarized descriptively. The maximum decline in PSA compared to baseline will be explored graphically. Further details will be provided in the TSAP.

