- 27. The randomization may take place up to 3 days prior to C1D1 if site procedures require advance randomization to accommodate the logistics of dispensing study medication to patients. Sites that use this option must include a copy of site policy/written justification in the ISF and submit a copy to the sponsor. If randomization is performed prior to C1D1, the subsequent visits must be scheduled with reference to C1D1.

Proprietary confidential information. © 2022 Boehringer Ingelheim International GmbH or one or more of its affiliated companies. All rights reserved.

FLOW CHART – PHASE II RANDOMISED TRIAL (FOR ALL PATIENTS AFTER APPROVAL OF PROTOCOL VERSION 10)

Study period		Cycle 3/				
Visits (V)	V1	V2	V3	V4	EOT ²	FU1 ³
Days (D)	D1 ±1	D8 ±1	D15 ±1	D22 ±1		EOT +42 (+7)
Tumour assessment / bone scans ⁸	X				X	X
Safety lab ⁷	X				X	X
Adverse event	X	X	X	X	X	X^4
Dispense enzalutamide ⁶	X					
Drug administration: Infusion BI 836845	X	X	X	X		
Drug administration: Enzalutamide	Con	tinuous daily o	losing			
Compliance check of enzalutamide	X				X	
Termination of trial medication					X	
Patient status						X
Patient completion ⁵						X

- 1. Treatment cycles: each treatment cycle consists of 28 days.
- 2. EOT: end of treatment visit; within 7 calendar days after permanent termination of trial drug(s). If permanent discontinuation of study drug falls on a scheduled visit, examinations as defined for EOT should be performed instead of the examinations of the scheduled visit.
- 3. FU: Follow-up visit: 42 days (+7) after permanent discontinuation of trial medication.
- 4. If not recovered at EOT, or new AE, or drug related death. After FU1 visit any AEs considered related to BI836845 must still be reported.
- 5. For more details on patient completion, see section 6.1.3.5
- 6. Enzalutamide may be dispensed either weekly or at the start of each cycle.
- 7. Safety labs: haematology, biochemistry, electrolytes, before dosing. See section 5.2.5 for details

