An exploratory expansion cohort will be pursued in approximately 25 enrolled patients to ensure 21 evaluable patients at the MTD, and/or recommended phase II dose (RP2D) determined in the escalation part of phase Ib described above. A patient is considered evaluable if data for the assessment of the primary endpoint is available. Patients recruited to this cohort will be on ongoing enzalutamide therapy and be beginning to show a rise in PSA (as described in section 3.3.2 inclusion #19) on this treatment at the time of consent for the expansion cohort of the study. These patients will continue to receive enzalutamide from the first day of treatment on the study combined with BI 836845. Patients in this expansion cohort will continue treatment until disease progression, undue toxicities, or discontinuation for any other reason, see section 3.3.4 for details.

Phase II - Randomised phase II:

In phase II, 80 patients will be randomised in a 1:1 ratio to receive treatment with either BI 836845 plus enzalutamide (Arm A) at the MTD, and/or the recommended phase II dose (RP2D) determined in phase Ib escalation, or enzalutamide alone (Arm B), in an open label, parallel group study design. Patients will continue treatment until disease progression, undue toxicities, or discontinuation for any other reason, see section 3.3.4 for details.

After discontinuation of all trial drugs and completion of the final follow up visit, see section 6.1.3, patients will be followed up further (every 90 days after the last follow up visit) for survival status in an observation period (until approval of protocol version 10 after which no further survival status will be collected).

Doc. No.: c02304008-15 Trial Protocol Version 12 Page 35 of 241

Proprietary confidential information. © 2022 Boehringer Ingelheim International GmbH or one or more of its affiliated companies. All rights reserved.

Phase I and Phase II:

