3.3.4.2 Discontinuation of the trial by the sponsor

Boehringer Ingelheim reserves the right to discontinue the trial overall or at a particular trial site at any time for the following reasons:

- 1. Failure to meet expected enrolment goals overall or at a particular trial site,
- 2. Emergence of any efficacy/safety information that could significantly affect continuation of the trial or any other administrative reasons.
- 3. Violation of GCP, the CTP, or the contract by a trial site or investigator, disturbing the appropriate conduct of the trial.
- 4. Discontinuation of the clinical development program with BI 836845 in CRPC.
 - As described in section 2.3 Benefit-risk assessment, topline results of 1280-0022 showed no added benefit of xentuzumab compared to placebo when treating participants with metastatic breast cancer. Consequently, the clinical development of xentuzumab (BI 836845) was discontinued by Boehringer Ingelheim in oncology generally, including in CRPC. Due to the worsening in benefit-risk and the discontinuation of the clinical development program with BI 836845 in CRPC, the trial will proceed towards termination based on the following 3 steps:
 - a. For xentuzumab-treated patients, the xentuzumab treatment will not extend past the drug expiration date (May 2023) of the last planned GMP manufacturing batch of IMP xentuzumab (provided that all patients are on xentuzumab for at least 2 years, and they

Doc. No.: c02304008-15 Page 44 of 241 Proprietary confidential information. © 2022 Boehringer Ingelheim International GmbH or one or more of its affiliated companies. All rights reserved.

are tolerating the drug without tumor progression). Patients that will discontinue xentuzumab can still be eligible for continued treatment with enzalutamide (standard of care in this setting) provided they are tolerating the drug without tumor progression.

- b. When all patients have discontinued xentuzumab treatment, if any patient on enzalutamide is able to continue taking this approved medication off study, then, at the request of the sponsor, the patient may end such treatment as part of the trial and discontinue study participation (if both the Investigator and patient agree).
- c. After all patients end treatment with all study drugs (xentuzumab and enzalutamide), the trial will be terminated.

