6.1.3.3 Follow-up period

The follow-up period starts immediately after permanent discontinuation of trial medication. All patients should have at least one follow-up visit 42 days (+7) after permanent discontinuation of trial medication which coincides with the EoR visit.

Additional follow-up visits should be performed in phases Ib and II (until approval of protocol version 10) for patients who withdrew for reasons other than progressive disease or start of further anti-cancer treatment; the additional visits will follow the usual tumour scan assessment schedule as per the Flow Chart, i.e. every 12 weeks from the start of trial.

Prior to approval of protocol version 10, follow-up period for every patient will end at the earliest of the following events

- Lost to follow-up
- Disease progression
- Start of a new anti-cancer therapy
- Death

After approval of protocol version 10, the follow up period for every patient will end after the first follow up visit.

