6.1.3.4 Observation period

Until approval of protocol version 10, all patients in the phase II randomised trial will be followed-up for overall survival every 90 days after the last follow-up visit (as specified in Section 6.1.3.3) until death, lost to follow-up or completion of the whole trial (as specified in Section 6.1.3.6) whatever occurs earlier. For patients who progressed on treatment, this period starts after the first follow up visit. For patients who have not progressed on treatment, this period starts after the last FU visit.

These visits may also be performed by telephone interview in case the patient is unable to visit the investigator.

The following information will be collected during the observation period:

- Date and method of contact
- Further treatment : regimen and drugs name, start and stop dates, reason for stopping this treatment
- Outcome death (date of and reason for death [if applicable])
- Follow-up of adverse events in case they were not yet recovered at the last FU visit.

Trial Protocol Version 12

Page 88 of 241

Proprietary confidential information. © 2022 Boehringer Ingelheim International GmbH or one or more of its affiliated companies. All rights reserved.

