6.1.3.6 End of whole trial

The trial will end when the last patient in both the phase Ib expansion and phase II has completed at least the last follow-up visit (as specified in Section 6.1.3.3) and an adequate number of overall survival events have been observed in phase II.

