5.2.2.3 Phase II

Progression-free survival (PFS) based on central review

The rules are the same as the ones described in Section 5.1.3, except the rule defined below. Instead of investigator assessment, the assessment based on central review will be used.

It should be referred to the imaging charter for more details regarding the assessment of response. However, there is one important change to RECIST 1.1 in the assessment of target lesions based on central review. In case one patient has the following:

- PR at last assessment
- more than 20% increase from nadir in the sum of longest diameters of target lesions, but less than 5 mm absolute increase from nadir.

In this case the assessment of PR should be carried forward to PR. This difference will not affect the endpoint PFS of this trial.

Overall survival (OS)

OS is defined as the time from randomisation until death from any cause.

For patients with 'event' as an outcome for overall survival:

• Overall survival [days] = date of outcome – date of randomisation + 1.

For patients with 'censored' as an outcome for overall survival:

• Overall survival (censored) [days] = date of outcome – date of randomisation + 1

The censoring rules for OS (i.e. outcome and date of outcome) are given in Table 5.2.2:3: 1.

Table 5.2.2.3: 1 Derivation rules for OS

Status at time of analysis	Outcome (event or censored)	Date of outcome
Patient died and the date of death is known	event	Date of death
Patient died and date of death is unknown	event	Date of last contact when the patient is known to be alive + 1 day
Patient alive	censored	Date of last contact when the patient is known to be alive
Unknown	censored	Date of last contact when the patient is known to be alive

The date when the patient was last known to be alive will be derived using the following data sources:

- Patient status: date of patient status obtained (if patient status is alive), last date patient known to be alive (in case patient is lost to follow-up), date of refusal (in case the patient actively refused to be followed up)
- Tumour assessment and/or radiological imaging data (date of imaging target lesions, date of imaging non-target lesions, date of detection of new lesion, date of assessment of bone lesions)
- Trial medication administration pages (including dates of start and end of administration, and termination of trial medication page)
- Onset and/or end dates of Adverse Events (AEs)

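### Survival collection stops at protocol version 10, but the overall survival update and the end-of-trial rule still look past that date, so a late update would censor informatively in the tail

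*Protocol*

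**What the plan says.** The current text (version 12) ends survival follow-up in several places. Section 3.1 keeps the observation period "until approval of protocol version 10 after which no further survival status will be collected". Section 6.1.3.4 says "Until approval of protocol version 10, all patients in the phase II randomised trial will be followed-up for overall survival every 90 days", and 6.2.3 limits the observation visits in the same way. Section 6.1.3.3 adds: "After approval of protocol version 10, the follow up period for every patient will end after the first follow up visit". The phase II flow charts for versions 10 and 12 have no observation column, and their last contact is defined by "FU: Follow-up visit: 42 days (+7) after permanent discontinuation of trial medication".

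Two sections still assume that survival follow-up continues. Section 7.3.2 gives the trigger for the second survival analysis: "The analysis will be updated once all patients have completed the last follow-up visit and/or when an adequate number of patients have died". Section 6.1.3.6 ends the trial when the last patient has had the last follow-up visit and "an adequate number of overall survival events have been observed in phase II". Neither document says what number is adequate. Section 3.3.4.2 step c has a different ending: "After all patients end treatment with all study drugs (xentuzumab and enzalutamide), the trial will be terminated".

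SAP 5.2.2.3 censors patients who are alive or of unknown status at "Date of last contact when the patient is known to be alive". That date is built from patient status, imaging, drug administration, adverse event, vital sign and subsequent-therapy records. The SAP is dated 28 September 2017, two years before version 10 (amendment 9, 13 September 2019), so it could not have set a version 10 cut-off.

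**The concern.** Overall survival is a named secondary endpoint in phase II, and 7.2 lists it among the endpoints on which inference rests. Before version 10, every phase II patient was contacted for survival whether treated or not. Afterwards, the records that feed the last-known-alive date arise routinely only for patients still on drug, up to the first follow-up visit 42 (+7) days after the last dose.

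If the update waits for the last follow-up visit, the two groups are treated differently. A patient who stopped drug before version 10 leaves the risk set at the last earlier contact, and a later death is not collected. A patient still on drug stays in the risk set, possibly for years. These patients are selected because they have not progressed or died. Being at risk late in the curve then depends on prognosis, which is informative censoring, and it may differ by arm.

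Separately, 6.1.3.6 makes closure depend on survival events that are no longer actively sought, and it does not match the sponsor's own termination steps.

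**Working it through.** **1. Nothing to reproduce for survival.** The documents give no target number of deaths, power or survival median. The check therefore compares the text and then bounds the effect under stated assumptions.

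**2. Two patients under the SAP rule, update at the last follow-up visit.**
- Patient 1 stopped drug before version 10 and was alive at the last 90-day contact. Outcome: censored at that contact, whatever happens later.
- Patient 2 is on drug at version 10. Outcome: visits, infusions and adverse event dates keep extending the last-alive date until the first follow-up visit after the last dose.

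No sentence in 7.3.2 or in the SAP brings Patient 2 back to the date that applies to Patient 1.

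**3. Scenario for the tail (assumptions, not in the documents).** 80 patients enter evenly over 12 months from January 2016. Version 10 falls at month 44 (September 2019) and the data end at month 88 (May 2023, the xentuzumab expiry date in 3.3.4.2). Survival is exponential with median m = 12 or 18 months. Of the patients alive at version 10, k = 2 or 4 are still treated.

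At version 10, time since entry runs from 32 to 44 months. Expected number alive = 80 × (m / ln 2) × (2^(−32/m) − 2^(−44/m)) / 12:
- m = 12: 80 × 17.31 × (0.1575 − 0.0787) / 12 = 9.1
- m = 18: 80 × 25.97 × (0.2916 − 0.1837) / 12 = 18.7

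Deaths missed by month 88 among off-treatment patients = (alive − k) × (1 − 2^(−44/m)):
- m = 12: 7.1 × 0.921 = 6.5 (k = 2); 5.1 × 0.921 = 4.7 (k = 4)
- m = 18: 16.7 × 0.816 = 13.6 (k = 2); 14.7 × 0.816 = 12.0 (k = 4)

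Kaplan-Meier estimate at 60 months, from simulation (1500 runs per scenario), against the true value 2^(−60/m):

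| Median | True | Treated patients have no later death, k = 2 / 4 | Treated patients share the common hazard |
|---|---|---|---|
| 12 months | 0.031 | 0.097 / 0.105 | 0.032 to 0.033 |
| 18 months | 0.099 | 0.202 / 0.210 | 0.097 to 0.103 |

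In the no-death case the curve stays at the height it had when follow-up of off-treatment patients ran out, between months 32 and 44. The last column shows that the error comes from the better prognosis of the retained patients. With an equal hazard there is almost none.

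**4. Effect on the planned statistics.** In the same scenarios the median was unchanged in every run. The mean log hazard ratio moved by less than 0.02, against a sampling standard deviation of about 0.25.

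**5. How many patients could be retained.** The exponential PFS rates in 7.6 are ln 2 / 4.6 = 0.151 and ln 2 / 3 = 0.231 per month. At 38 months, the mean time to version 10 in this scenario (44 − 6), the number still progression-free is 40 × exp(−0.151 × 38) = 0.13 in Arm A and 40 × exp(−0.231 × 38) = 0.006 in Arm B.

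A second simulation put version 10 at 24 to 40 months after first randomisation, with an assumed median of 6 to 15 months from progression to death and drug stopped at progression. Patients still treated fell from about 3.0 to 0.3 in Arm A and from about 0.8 to 0.02 in Arm B. Between 2.5 and 21 patients in Arm A and between 1.7 and 21 in Arm B were off treatment, alive and no longer followed. Fewer than 0.5 later deaths per arm would be caught by the first follow-up visit.

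**The case against.** The strongest reply is section 2.2. It says the data already suffice for the primary and secondary objectives, limits later collection to safety needs, and sends it to a revised report. On that reading the event limb of the 7.3.2 trigger was already met, and the event condition in 6.1.3.6 may have been too, in which case what remains of 6.1.3.6 fits with step c. This is a fair reading, and no passage says that safety records after version 10 will feed a survival analysis. It does not close the gap. Section 2.2 sets no survival cut-off, 7.3.1 puts information gathered after the primary cut-off into a revised report, and 7.3.2 still offers the last-visit limb.

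A reader might infer that survival information after version 10 comes strictly from patients on drug. That goes too far. The version 10 and 12 flow charts still tick patient status at the first follow-up visit (6.2.3 lists it only for visits before version 10), and 3.3.4.1 allows a death to be reported after consent is withdrawn. Neither replaces regular survival contact.

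A reader might also infer that late survival will be roughly doubled, or that the survival comparison is invalid. The documents do not support either. The retained patients and their absence of deaths are assumptions, the planned PFS rates imply almost no one left on drug, and section 2.3 records a recommendation to stop xentuzumab from 19 October 2021. No 60-month rate is a planned output, and the trial is declared exploratory. The silence of the 2017 SAP on version 10 is not a fault.

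**Conclusion.** The inconsistency is real and stands in the current text. Survival collection ends at version 10, yet 7.3.2 permits an update at the last follow-up visit and 6.1.3.6 keeps a survival-event condition that 3.3.4.2 step c does not have. If the last-visit limb is used with the SAP rule, late censoring is informative and the tail of the Kaplan-Meier curve may be too high.

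The consequence is limited. Early survival and the median are unaffected and the hazard ratio almost so. The 60-month figures of about 0.10 against 0.03, and 0.20 to 0.21 against 0.10, illustrate an extreme: they need 2 to 4 phase II patients still treated at version 10 and no deaths among them. The documents give neither the number treated nor their survival, so the actual size is unknown and could be close to nil.

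**What to change.** - In 7.3.2, and in a revision of SAP 5.2.2.3, set a survival data cut-off for phase II no later than approval of version 10 at each site.
- Censor patients not known to have died by then at their last contact known alive on or before the cut-off. Do not censor at the cut-off itself when the last contact was earlier, because that credits survival time nobody observed and departs from the SAP table.
- Exclude alive dates and deaths after the cut-off from the survival analysis.
- Delete the last-follow-up-visit trigger in 7.3.2.
- Reconcile the survival-event condition in 6.1.3.6 with 2.2, 3.1 and 3.3.4.2 step c, either by stating that it was met by version 10 and with how many deaths, or by removing it.

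The cost is wording in two protocol sections and one SAP rule, with no new visits or data. A few late patient-months on treatment are not used, and the survival curve ends earlier.
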